## 5.3 Summary of Potential Risks and Benefits

The potential benefits of study participation are that mGluRs mutation-positive subjects with ADHD (1) may experience a reduction in symptoms as a result of treatment with NFC-1 and (2) will understand that they are contributing to the scientific knowledge that may lead to expansion of the treatment options for patients with genetic disorders impacting mGluRs together with ADHD. No other benefits of participation are anticipated.

The potential risks of study participation include those associated with exposure to NFC-1 and the risks of medical evaluation, including venipuncture.

A summary of the pharmaceutical properties and known potential risks of NFC-1 is provided in the current version of the IB (1). The investigator must become familiar with all sections of the NFC-1 IB before the start of the study.

#### 6. OBJECTIVES

The objectives of this study are:

- To assess the efficacy of NFC-1 relative to placebo in reducing the severity of symptoms associated with ADHD in adolescents with genetic disorders impacting mGluRs.
- To obtain additional safety data following exposure to NFC-1 in this population.

## 7. STUDY DESIGN

#### 7.1 Overall Study Design and Plan

This is a randomized, double-blind, placebo-controlled, parallel-group phase 2 study of adolescents to compare the safety and efficacy of NFC-1 with that of placebo. Approximately 90 male and female subjects will receive randomized treatment with NFC-1 or placebo to obtain 80 subjects that complete the study as planned. Subjects must be  $\geq 12$  to  $\leq 17$  years of age and have ADHD as defined by the Diagnostic and Statistical Manual of Mental Disorders,  $5^{th}$  edition (DSM-5) and Version 5 of the Attention Deficit Hyperactivity Disorder Rating Scale (ADHD-RS-5)  $\geq 28$  at Baseline with or without conventional ADHD therapy.

Subjects will not be eligible if they are mentally or legally incapacitated, have significant emotional problems, have a prior diagnosis of co-morbid major psychiatric disorders or any clinically significant medical condition that would interfere with the conduct of study evaluations, are pregnant or nursing, and/or have abnormal laboratory values that indicate clinically significant endocrine, gastrointestinal, cardiovascular, hematological, hepatic, immunological, renal, respiratory, or genitourinary abnormalities or diseases.

As shown in Figure 7.1, subjects will be randomly assigned to receive either NFC-1 or placebo on Day -1 and will start taking the investigational product (IP) at a dose of 100 mg twice daily on Day 1. Dosing will be optimized to 100 mg, 200 mg, or 400 mg twice daily, as appropriate, over the 4 weeks of treatment (dose optimization phase), based on clinical response and tolerability. If the subject tolerates a dose well, the dose will be maintained for an additional 2 weeks (dose maintenance phase) when the primary assessments of efficacy and tolerability will be performed. A follow-up telephone call will be performed at Week 7.

Confidential

Approximately 45 subjects will be randomly assigned to each treatment group. The duration of study participation is expected to be 70 days.

Efficacy will be assessed by the ADHD-RS-5 score, CGI-I, CGI-S, Adolescent Sleep Hygiene Scale (ASHS), and Screen for Childhood Anxiety-related Emotional Disorders (SCARED).

Safety will be assessed by evaluating AEs, physical examination findings, vital sign measurements, electrocardiograms (ECGs), clinical laboratory test results, and Columbia Suicide Severity Rating Scale (C-SSRS) scores.

All AEs observed by the study personnel or reported by the subject during the study (from the time of the signing of the informed consent through the posttreatment visit) will be documented.

[figure not shown]

Figure 7.1: Study Design

Abbreviation: ET = early termination

## 7.2 Discussion of Study Design

The randomized, double-blind, parallel group design chosen for this study is standard for the head-to-head comparison of treatments. After assessing the baseline status of the disease (in the absence of study drug), the 4-week dose titration paradigm allows for individualized dose optimization. This is the norm for pharmacological interventions in neuropsychiatric indications. The subsequent 2-week maintenance period will allow stabilization of drug effect(s) prior to assessing the disease status at the end of the treatment (ie, the primary endpoint in this study).

## 7.3 Study Site(s)

The study will take place at approximately 35 sites in the United States. Each site is anticipated to screen a sufficient number of subjects to be able to randomize approximately 2-3 subjects. A study site with a high recruitment rate may be allowed to recruit more subjects if other sites have slow enrollment.

#### 8. SUBJECT POPULATION

## 8.1 Selection of Study Population

Approximately 90 subjects will be randomized. It is anticipated that this will yield 80 subjects who will have completed the study as planned. Justification of this sample size is presented in Section 13.2.

A screening log of potential study candidates and an enrollment log of enrolled subjects must be maintained at each study site.

## 8.2 Study Entry Criteria

#### 8.2.1 Inclusion Criteria

A subject will be eligible for study participation if the subject meets all of the following criteria:

- 1. Subject is male or female,  $\geq 12$  to  $\leq 17$  years of age.
- 2. Subject has a body mass index in the range of  $\geq 15$  to  $\leq 35$  kg/m^2.
- 3. Subject has ADHD as defined by DSM-5 and ADHD-RS- $5 \ge 28$  at Baseline with or without conventional ADHD therapy.
- 4. Subject has an intelligence quotient (IQ) > 79, based on the Wechsler Abbreviated Scale of Intelligence, second edition (WASI-II).
- 5. Subject has been genotyped previously and determined to have disruptive mutations in genes within the GRM-network as determined by the presence of CNVs (GRM biomarker-positive subjects). The confirmation of a subject's positive status will be provided by the sponsor.
- 6. Subject is a non-smoker and/or has not used nicotine or nicotine-containing products on a weekly or more frequent basis for at least approximately 6 months.
- 7. Subject is judged to be in general good health, other than having ADHD, based on medical history, physical examination, vital signs measurements, laboratory safety tests, and the C-SSRS performed at the Screening Visit and/or prior to administration of IP.
- 8. Female subjects of reproductive potential will have a negative pregnancy test at Screening (serum) and prior to drug administration (urine). If sexually active, female subjects agree to use (and/or have her partner use) 2 acceptable methods of birth control beginning at least 2 weeks prior to administration of IP and throughout the study. Acceptable methods of

- birth control are abstinence or 2 of the following: intrauterine device, diaphragm, spermicides, cervical cap, contraceptive sponge, and condoms.
- 9. Subject has no clinically significant abnormality on ECG performed at the Screening Visit and/or prior to administration of IP such as serious arrhythmia, bradycardia, tachycardia, cardiac conduction problems, or other abnormalities deemed to be a potential safety issue.
- 10. Parent/legal guardian and subject understand the study procedures and agree to the subject's participation in the study as indicated by parental/legal guardian signature on the subject informed consent form and subject signature on the assent form.

#### 8.2.2 Exclusion Criteria

A subject will be excluded from the study if the subject meets any of the following criteria:

- 1. Subject or parent/legal guardian is in the opinion of the investigator mentally or legally incapacitated, has significant emotional problems at the time of the Screening Visit or during the conduct of the study.
- 2. Subjects with a current or relevant history of comorbid major psychiatric disorders (ie, aside from ADHD), including major depression, bipolar disease, schizophrenia, pervasive development disorder, and intellectual disability.
- 3. Subject is currently taking a prohibited medication and/or is unwilling to wean off current ADHD medication to participate in the study.
- 4. Subject has a history of any illness that in the opinion of the study investigator might confound the results of the study or poses an additional risk to the subject by his or her participation in the study.
- 5. Subject has a history of any clinically significant disease that is not currently clinically stable. Subjects with a history of uncomplicated kidney stones may be enrolled in the study at the discretion of the investigator.
- 6. Subject has a known history or presence of syncope, cardiac conduction problems (eg, clinically significant heart block), exercise-related cardiac events including syncope and pre-syncope, or clinically significant bradycardia.
- 7. Subject has a history of stroke, chronic seizures, or major neurological disorder which, in the opinion of the investigator, would interfere with the subject's ability to participate and/or be evaluated in the study.
- 8. Subject is pregnant or a nursing mother.
- 9. Subject has a history of aversion to blood draws that in the opinion of the investigator or parents would result in compromising the study conduct.
- 10. Subject has a history of physiologic difficulty in venous access that in the opinion of the investigator and parent/legal guardian would compromise study conduct.
- 11. Subject has a history of inability to swallow whole unadulterated capsules, which in the opinion of the investigator or parent/legal guardian would compromise study conduct.
- 12. Subject has a systolic or diastolic blood pressure  $\geq$  the 95th percentile for his or her age.
- 13. Subject consumes any alcoholic beverages on a regular basis (weekly or more often).
- 14. Subject consumes excessive amounts of caffeine, defined as greater than 4 servings (1 serving is approximately equivalent to 120 mg of caffeine) of coffee, tea, cola, or other caffeinated beverages per day.

- 15. Subject has a history of significant multiple and/or severe allergies, or has had an anaphylactic reaction or significant intolerability to prescription of nonprescription drugs or food
- 16. Subject is currently a regular user (including "recreational use") of any illicit drugs (including marijuana) or has a history of drug (including alcohol) abuse.
- 17. Subject has had surgery, lost more than 5 mL/kg of blood, or participated in another investigational drug trial within 4 weeks prior to the Screening Visit.
- 18. Subject has a clinical laboratory abnormality that indicates clinically significant hematologic, hepatobiliary, or renal disease:
  - a Aspartate aminotransferase/serum glutamic oxaloacetic transaminase > 2.0-times the upper limit of normal
  - b Alanine aminotransferase/serum glutamic pyruvic transaminase > 2.0-times the upper limit of normal
  - c Total bilirubin > 2.0-times the upper limit of normal
  - d Hemoglobin < 9 g/dL
  - e White blood cell count < 1,000/mm^3
  - f Platelet count < 100,000/mm^3
  - g Creatinine kinase > 300 U/L for females and > 500 U/L for males

## 8.3 Premature Subject Withdrawal

All subjects will be advised that they are free to withdraw from participation in this study at any time, for any reason, and without prejudice. Every reasonable attempt should be made by the investigator to keep subjects in the study; however, subjects must be withdrawn from the study if they withdraw consent to participate. Investigators must attempt to contact subjects who fail to attend scheduled visits by telephone or other means to exclude the possibility of an AE being the cause of withdrawal. Should this be the cause, the AE must be documented, reported, and followed as described in Section 11.2.

The sponsor reserves the right to request the withdrawal of a subject due to protocol violations or other reasons.

The investigator also has the right to withdraw subjects from the study at any time for lack of therapeutic effect that is intolerable or otherwise unacceptable to the subject, for intolerable or unacceptable AEs, intercurrent illness, noncompliance with study procedures, administrative reasons, or in the investigator's opinion, to protect the subject's best interest.

If a subject is withdrawn before completing the study, the reason for withdrawal and the date of discontinuation will be recorded on the appropriate electronic case report form (eCRF). Whenever possible and reasonable, the evaluations that were to be conducted at the completion of the study should be performed at the time of premature discontinuation.

## 8.4 Subject Replacement Criteria

Once randomized, subjects who discontinue from the study will not be replaced.

#### 9. TREATMENTS

## 9.1 Identification of Investigational Product(s)

The following IPs will be used in this study:

- NFC-1 will be provided as white opaque size-2 capsules containing 100 mg or 200 mg NFC-1; no excipients are used.
- Dose, route, and frequency (NFC-1): 100 mg, 200 mg, and 400 mg administered orally twice daily in the fed or fasting state.
- Matching placebo will be provided as white opaque size-2 capsules containing microcellulose instead of NFC-1.
- Dose, route, and frequency: Placebo for 100 mg, 200 mg, and 400 mg administered orally twice daily in the fed or fasting state.

## 9.2 Labeling and Packaging

All packaging and labelling operations will be performed by the sponsor according to Good Manufacturing Practice and Good Clinical Practice (GCP) rules. The IP will be sent to the study site by the sponsor or designee. Labelling will be in local language and dependent upon local regulations.

## 9.2.1 Labeling

The bottle will have affixed a label that meets the applicable regulatory requirements and may include the following: subject identifier, name of compound or placebo, dosage strength, lot identifier, protocol number, specified number of capsules, caution statement ("New Drug – Limited by United States Law to Investigational Use"), storage conditions, and sponsor identification.

The investigator will be asked to save all empty packaging or packaging containing unused capsules for final disposition by the sponsor.

#### 9.2.2 Packaging

NFC-1 and placebo will be supplied by the sponsor. NFC-1 will be packaged in high-density polyethylene bottles of 20 capsules. NFC-1 and placebo will be packaged so that the investigator, the study clinic personnel, and subjects are blinded to study treatment.

## 9.3 Treatments Administered

Eligible subjects will be randomized to either NFC-1 or placebo for 6 weeks of treatment; a 4-week stepwise dose-optimization period will be followed by a 2-week maintenance period.

NFC-1 or placebo will be administered twice daily for a maximum of 6 weeks. At Baseline, randomized subjects will receive blinded IP to begin treatment the following day at a dose of 100 mg twice daily. Doses will be optimized to 100 mg, 200 mg, or 400 mg twice daily over the following 4 weeks as determined by the investigator's assessment of clinical response and tolerability to IP. Additional dose adjustments will not be allowed after Week 4, and if well tolerated, subjects will be maintained at their Week-4 dose.

The objective of this period is to ensure subjects are titrated to an optimal dose of IP based upon the investigator's review of efficacy, AEs, and clinical judgment.

Version: Final Version v4.0

Page 24 of 58

## 9.4 Dispensing and Storage

The IP supplied by Medgenics is to be used exclusively in this clinical study according to the instructions of this protocol. The investigator is responsible for dispensing the IP according to the dosage scheme and for ensuring proper storage of the IP.

The investigator must confirm the receipt of the IP with his/her signature. A copy of this receipt must be kept by the investigator, and another copy will be stored at Medgenics and/or . Until the IP is dispensed to the subjects, it must be stored at 20-25°C and in a dry place in a securely locked area that is not generally accessible.

The key to the storage area is to be kept by the investigator or designee responsible for the IP. The storage area will be accessible only to those persons authorized by the investigator to dispense the IP.

## 9.4.1 Interactive Web Response System for Investigational Product Management

An Interactive Web Response System (IWRS) will be employed in this study to register and randomize subjects, maintain the blind during the study, provide a mechanism for unblinding, dispense and manage investigational product, and track final subject disposition (ie, study completion or discontinuation).

A user manual with specific functions and instructions for the IWRS will be provided to the site.

## 9.5 Method of Assigning Subjects to Treatment Groups

In this parallel-group randomized study, subjects who meet study entry criteria will be randomly assigned in a 1:1 ratio to NFC-1 or placebo. The randomization schedule will be computergenerated using a permuted block algorithm and will randomly allocate IP to randomization numbers. The randomization numbers will be assigned sequentially through the central IWRS as subjects are entered into the study.

The randomization schedule will be prepared by in advance of study initiation. All efforts will be made to ensure the integrity of the study blind up until the final database has been locked. No one involved in study conduct will have access to the randomization schedule prior to that event. No subject will be randomized into this study more than once.

## 9.6 Blinding and Unblinding Treatment Assignment

All subjects, investigators, and study personnel involved in the conduct of the study, including data management, will be blinded to treatment assignment with the exception of a specified unblinded statistician from who will have access to the randomization code. The unblinded study personnel will not otherwise participate in study procedures or data analysis prior to unblinding of the study data to all study related personnel.

Study personnel will endeavor to safeguard the integrity of the study blind to minimize bias in the conduct of the study. Treatment unblinding is discouraged if knowledge of the treatment assignment will not materially change the planned management of a medical emergency. Unblinding will be permitted in a medical emergency that requires immediate knowledge of the subject's treatment assignment. Unblinding should be discussed in advance with the medical monitor if possible. For emergency unblinding, study personnel will access the IWRS unblinding module. If the investigator is not able to discuss treatment unblinding in advance, then he/she must notify the medical monitor as soon as possible about the unblinding incident without revealing the subject's treatment assignment. The investigator or designee must record the date and reason for study discontinuation on the appropriate eCRF for that subject. In all

cases that are not emergencies, the investigator should discuss the event with the medical monitor prior to unblinding the subject's treatment assignment.

If treatment assignment is unblinded for an individual subject, study personnel will be notified of that subject's treatment assignment without unblinding the treatment assignments for the remaining subjects in the study. Thus, the overall study blind will not be compromised. If a subject's treatment assignment is unblinded, he/she may or may not be asked to withdraw from the study. The investigator will make this decision after consultation with the medical monitor.

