## 10.3.2 Efficacy

All scales included in Section 10.3.2 that are described as "clinician rated" are to be completed by the principal investigator or a delegated subinvestigator who is a licensed clinician. A licensed clinician is defined as a doctor of medicine, doctor of osteopathic medicine, or licensed psychologist with a PhD or another individual that is approved by the sponsor or designee. All raters are to be approved by the sponsor or designee.

## 10.3.2.1 Attention Deficit Hyperactivity Disorder Rating Scale Version 5

The ADHD-RS-5 (7) will be used as the primary measure. This parent-reported clinician-rated scale will be administered at each visit, beginning at Screening to capture the ADHD symptoms within each study week. The ADHD-RS-5 is a parent-reported/clinician-rated scale that was developed to measure the behaviors of children with ADHD, and comes in a Home Version and a School Version, with separate forms for children (ages 5-10 years) and adolescents (11-17 years); it consists of 18 items designed to reflect the symptomatology of ADHD based on the Diagnostic and Statistical Manual of Mental Disorders (DSM) DSM-5 criteria. Each item will be scored on a range of 0 (reflecting no symptoms) to 3 (reflecting severe symptoms) with total scores ranging from 0-54. The 18 items may be grouped into 2 subscales: inattention and hyperactivity/impulsivity. The Inattention subscale raw score is computed by summing the item scores for Items 1–9. The Hyperactivity–Impulsivity subscale raw score is computed by summing the item scores for Items 10–18. Additionally, the ADHD-RS-5 incorporates 2 impairment scales keyed to the inattention and hyperactivity–impulsivity dimensions, which allow the clinician to assess the extent to which ADHD-related problems adversely affect the home and/or school functioning of children and adolescents

Time of administration: 10-15 minutes

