8 EFFICACY ANALYSIS

8.1 Primary Analysis

The primary efficacy endpoint will be the change in ADHD-RS-5 total score from Baseline to the end of treatment (e.g., Visit 8). For any subjects who discontinue the study prior to Visit 8, their last treated value of the ADHD-RS-5 will be used. That is, the LOCF method of imputation will be employed. The analysis will be performed on the ITT population using an analysis of covariance (ANCOVA) model. The model will use a residual (restricted) maximum likelihood (REML) estimation method and a standard variance components (VC) covariance structure, with treatment group (NFC-1 or placebo) as a fixed factor and baseline ADHD-RS-5 total score as a covariate. The null hypothesis is that there are no differences between the means of the two treatment groups. The hypothesis will be tested at a two-tailed alpha of 0.05. This analysis will be repeated for each of the scheduled visits for ADHD-RS-5 and summarized within the table. Descriptive summaries for actual and change from baseline values will be displayed along with the LS means, LS mean treatment difference, and 95% CIs of the treatment difference, and p-values by visit.

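### Protocol 9.6 lets an individual code break be disclosed to study personnel without excluding the raters, so a primary rating can be made by someone who knows the arm, and the SAP has no provision for it

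*Protocol*

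**What the plan says.** Protocol 9.6 blinds investigators and study personnel, discourages unblinding that would not change emergency management, and asks that non-emergency cases be discussed with the medical monitor first. On what follows an individual code break it says:

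- Disclosure: "If treatment assignment is unblinded for an individual subject, study personnel will be notified of that subject's treatment assignment". The sentence goes on to say that the other subjects' assignments stay concealed.
- Medical monitor: where an emergency break could not be discussed beforehand, the monitor is told "as soon as possible about the unblinding incident without revealing the subject's treatment assignment".
- Record: the investigator or designee "must record the date and reason for study discontinuation on the appropriate eCRF".
- Continuation: "If a subject's treatment assignment is unblinded, he/she may or may not be asked to withdraw from the study". On who decides: "The investigator will make this decision after consultation with the medical monitor".

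Under Protocol 10.3.2, clinician-rated scales are "completed by the principal investigator or a delegated subinvestigator who is a licensed clinician". The ADHD-RS-5, the primary measure, is described there as parent-reported and clinician-rated, and the CGI scales as the investigator's global assessment. Protocol 9.9 and 10.1.3.1 have the investigator judge response and set the dose during optimization. Protocol 8.3 asks, where possible, for end-of-study evaluations when a subject is withdrawn.

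SAP 8.1 states: "The analysis will be performed on the ITT population using an analysis of covariance (ANCOVA) model". For subjects who stop early it carries forward the last on-treatment ADHD-RS-5 value. It has no rule for ratings made after a code break.

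**The concern.** The primary outcome depends on a clinician's judgement of a parent's report, so it is open to influence from knowledge of the treatment. Protocol 9.6 names a broad group to be told the arm, and the raters belong to that group. No section provides an independent rater or a change of rater after a code break. During dose optimization the person told may also be the one choosing the dose.

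The assurance in 9.6 that the overall blind survives rests on the remaining subjects staying concealed. It does not protect the ratings of the subject whose code was broken. Those ratings enter the intention-to-treat comparison with the same weight as blinded ones, and no planned analysis shows whether they matter.

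**Working it through.** The plan gives no figure on this point: no expected number of code breaks and no size of rating bias. The check is therefore a reading of the sections together, followed by an illustration on labelled assumptions.

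**Reading the sections together**

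1. Who is told: study personnel, without restriction (Protocol 9.6).
2. Who rates: the investigator or a delegated subinvestigator (Protocol 10.3.2). These people are study personnel.
3. Can the subject go on being rated? Yes, because withdrawal is optional (9.6). If the subject is withdrawn, Protocol 8.3 still asks for the final evaluations. SAP 8.1 may then use that rating as the carried-forward value, so withdrawal alone does not close the route.
4. Is the break recorded? The SAE report asks whether and when the investigator was unblinded, if that is available (Protocol 11.2.6.1). For a code break without an SAE, the only eCRF instruction in 9.6 concerns study discontinuation. No field is specified for the date of unblinding or for who else was told.
5. Does 9.6 agree with itself? The eCRF instruction presumes that the subject has discontinued, while the next paragraph says that "he/she may or may not be asked to withdraw from the study". The two do not fit.

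**Size, as an illustration**

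Inputs: 45 per arm (Protocol 7.1); effect size 0.7 (Protocol 13.2, SAP 5.1); SD of change 10 points (assumed); k affected subjects in one arm, each with b points of bias in the same direction (assumed). Baseline adjustment is ignored.

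- Implied effect = 0.7 × 10 = 7 points.
- Shift in the arm mean = k × b / 45.
- Share of the effect = shift / 7.

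| k | b (points) | Shift (points) | Share of 7 points |
|---|---|---|---|
| 1 | 5 | 5/45 = 0.11 | 1.6% |
| 2 | 10 | 20/45 = 0.44 | 6.3% |
| 4 | 10 | 40/45 = 0.89 | 12.7% |

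For the first row, the share is 5 / (45 × 0.7 × SD). An SD of 5 would double it to 3.2%, and an SD of 20 would halve it to 0.8%.

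The effect on the two-sided 5% type I error comes from the noncentral t distribution with 88 degrees of freedom and noncentrality s × √(45/2), where s is the shift in SD units:

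- One subject in one arm, bias 0.5 SD: s = 0.5/45 = 0.011, error 5.03%.
- Two subjects in each arm, bias 1 SD favouring NFC-1 in both: s = 4/45 = 0.089, error 7.0%.
- Five subjects in each arm, bias 1 SD favouring NFC-1 in both: s = 10/45 = 0.222, error 18.1%. This needs 10 of 90 subjects to be affected, and nothing in the documents suggests that.

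**The case against.** The strongest reply is that this will hardly ever happen. Unblinding is discouraged, non-emergency breaks need prior discussion with the medical monitor, and Protocol 11.2.4 says unblinding is unnecessary in most circumstances even after an SAE. The 30-subject adolescent study in Protocol 5.2 reported no treatment-related SAEs. This stands, and it keeps the size small.

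A second reply is that the notification sentence may mean only that a code break reveals one subject's code and no others. That reading is possible. However, the text does not say who may be told, and it does not keep raters out. Section 9.6 also bars unblinded personnel from study procedures, but that sentence follows the exception for the unblinded statistician and does not clearly bind site staff told after a code break.

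Some stronger readings are tempting, and the documents do not support them:

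- That affected ratings cannot be identified. The SAE report requests the date of investigator unblinding, and an emergency that justifies a code break would often be an SAE. The gap is limited to other code breaks and to other people told.
- That 9.6 contradicts itself by withholding the arm from the medical monitor while giving it to study personnel. These are different recipients, and both rules can be followed.
- That the investigator alone decides whether the subject stays. The decision follows consultation with the medical monitor.
- That the bias could plausibly reach 13% of the effect. The arithmetic is right, but it needs 4 of 45 subjects in one arm, each biased by 10 points, which is more than the whole implied effect of 7.
- That SAP 7.2 is at fault for not listing unblinding as a deviation. A code break allowed by 9.6 is not itself a deviation, and the list includes a category for other deviations.

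**Conclusion.** The concern holds as a defect in the written procedure. As Protocol 9.6 and 10.3.2 stand, a primary rating can be made by someone who has been told the arm, whether the subject stays in or is rated at early termination, and SAP 8.1 treats that rating like any other. The separate mismatch in 9.6, between recording a discontinuation and leaving withdrawal open, is plain on the text.

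The likely effect on the result is small: 0.11 points, or 1.6% of the implied effect, for one subject with 5 points of bias. That figure rests on an assumed SD of 10 and an assumed bias. The number of code breaks is unknown but should be low. A reader might infer that the trial's blind as a whole is unsafe. The documents do not support that, because only the subject whose code is broken is affected. The change is worth making because it removes an avoidable source of bias at very little cost. Whether an unblinded subject should stay in the study is a clinical decision and is not judged here.

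**What to change.** **Protocol 9.6**

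- Replace the notification sentence. The assignment goes only to those who need it to manage the event, and not to the ADHD-RS-5 or CGI raters where these are different people.
- Where the site already has another approved rater who is still blinded, that rater makes the later ratings. Sites expect about 2–3 subjects each (Protocol 7.3), so some may have no such rater. The person managing the event may also be the only rater. The sensitivity analysis below covers both cases, so no new staff are required.
- Record the date, reason and recipients of every code break in the eCRF, whether or not the subject leaves the study.
- Reconcile the instruction to record study discontinuation with the sentence that leaves withdrawal open.

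**SAP 8.1**

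- Keep the intention-to-treat ANCOVA as the primary analysis.
- Add one sensitivity analysis with the same model. Any ADHD-RS-5 rating made after a code break by a person who knows the arm is set to missing, and the last rating made before the code break is carried forward.

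The cost is a few sentences, one eCRF entry and one extra model run. With only one or two affected subjects the sensitivity result will differ little from the primary one, but it puts the size of the problem on record.
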